8.2. Adverse Events

8.2.1. Adverse Event Definitions

A TEAE is any AE either reported for the first time or worsening of a pre-existing event after first administration of study drug and within 30 days of the last dose of study drug. Analysis of AEs (as discussed below) will be limited to TEAEs, but data listings will include all AEs regardless of their timing in relation to study drug administration.

Adverse events will be tabulated by MedDRA PT and SOC. Severity of AEs will be graded using the NCI CTCAE. The CTCAE v5 is used for this study. The CTCAE reporting guidelines and grading details are available on the Cancer Therapy Evaluation Program website.

The subset of AEs considered by the investigator to be related to study drug will be considered to be treatment-related AEs. The incidence of AEs and treatment-related AEs will be tabulated. Serious AEs will also be tabulated.

Any missing onset date, causality, or severity must be queried for resolution. Unresolved missing causality and severity will be handled according to the following rules:

- An unresolved missing causality will be considered treatment-related.
- An unresolved missing severity will be identified as an unknown severity.

For purposes of analysis, all AEs will be considered TEAEs unless the AE can unequivocally be defined as not treatment-emergent.

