6.7.1. Permitted Medications and Procedures

6.7.1.1. Pneumocystis jirovecii Pneumonia Prophylaxis

All participants will receive a PJP prophylaxis regimen determined by the investigator. Examples of standard PJP prophylaxis therapies include trimethoprim-sulfamethoxazole, atovaquone, dapsone with or without pyrimethamine, and pentamidine (National Comprehensive Cancer Network 2017). Due to reports of cross-sensitivity between sulfonamides and dapsone, all participants who have a known or suspected allergy to sulfonamides must receive either inhaled pentamidine or atovaquone for PJP prophylaxis. If inhaled pentamidine or atovaquone are not available, the participants should not be enrolled. Prophylaxis should be given while participants are receiving study drug and should continue for at least 2 to 6 months after the last dose of study drug.

The prophylactic agents will be obtained from commercial supplies and will be reimbursed by the sponsor. Investigators are responsible for ensuring that participants receive commercially available supplies of the selected prophylactic agents as required per Protocol. The sponsor may provide prophylactic agents where required by applicable law or regulation or under other limited circumstances when a participant may not otherwise have access to these therapies. The contents of the label will be in accordance with all applicable regulatory requirements. Further details are available in the Pharmacy Manual.

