8.9.2. Additional Follow-Up Period

Participants will have additional follow-up assessments for 12 weeks (3 months) after EOT. Safety follow-up is included in this 12-week (3 months) additional follow-up period. The following information will be collected:

- The start date of new AIHA therapy.
- Type of therapy.
- Marker for hemolysis.

If the participant withdraws consent for study drug but continues in the follow-up period of the study, the above information will also be collected.

The site will also use continuing participant records to supply data on subsequent treatment regimens and disease activities in the eCRF.

For participants who receive study drug in the extension period, the safety follow-up is included in the 12-week (3-month) additional follow-up period and should occur 30 to 35 days after the last dose of study drug.

9. ADVERSE EVENTS: DEFINITIONS AND PROCEDURES FOR RECORDING, EVALUATING, FOLLOW-UP, AND REPORTING

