10.4.2. Safety Analyses

10.4.2.1. Adverse Events

A treatment-emergent adverse event is any AE either reported for the first time or worsening of a pre-existing event after first dose of study drug. Analysis of AEs will be limited to TEAEs, but data listings will include all AEs regardless of their timing to study drug administration. Adverse events will be tabulated by the MedDRA preferred term and system organ class. Severity of AEs will be based on the NCI CTCAE v5.0 using Grades 1 through 4.

The subset of AEs considered by the investigator to have a relationship to study drug will be considered to be treatment-related AEs. If the investigator does not specify the relationship of the AE to study drug, the AE will be considered treatment-related. The incidence of AEs and treatment-related AEs will be tabulated.

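### The SAP ends the treatment-emergent window 30 days after last dose where the protocol sets no end, does not declare the change, and plans no summary of later events

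*SAP*

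**What the plan says.** **Protocol 10.4.2.1** reads: "A treatment-emergent adverse event is any AE either reported for the first time or worsening of a pre-existing event after first dose of study drug". It gives no closing date and adds: "Analysis of AEs will be limited to TEAEs, but data listings will include all AEs".

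**SAP 8.2.1** closes the window: the event must be new or worsen "after first administration of study drug and within 30 days of the last dose of study drug". It then makes the same restriction, "Analysis of AEs (as discussed below) will be limited to TEAEs", while "data listings will include all AEs regardless of their timing in relation to study drug administration".

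**Follow-up.** Protocol 8.9.2: "Participants will have additional follow-up assessments for 12 weeks (3 months) after EOT". Protocol Table 1 schedules AE assessment at Months 1, 2 and 3 after treatment, and Table 2 does the same after the extension. Protocol 4.1 and SAP Sections 1 and 3 name safety as one purpose of this follow-up.

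**Declared changes.** SAP 10.1 lists three departures from the protocol: the response definitions, the treatment extension population and the interim analysis. SAP 10.2.1 names Sections 8.1, 8.2.2 and 8.3.1 as amended, but not 8.2.1; only its catch-all for minor changes could cover it.

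**The concern.** Safety is a primary objective, and the protocol goes on collecting AEs for about three months after treatment. If the tables stop at day 30, a reader of the study report sees incidence figures that do not follow the protocol's definition, and nothing in the SAP says so. Events from the later part of follow-up would have to be found and counted by hand in listings.

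The AESI list in SAP 8.2.2 includes *Pneumocystis* pneumonia (PJP). For that infection the protocol has prophylaxis that "should continue for at least 2 to 6 months after the last dose of study drug", so it does not treat day 30 as the end of concern. The contrast within the SAP is also awkward: Section 5.1 has by-visit analyses include follow-up data, so a late laboratory value is summarised while a late AE is not.

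**Working it through.** **1. The plan's own safety figure.** Protocol 10.1 and SAP 3.3 give the chance of at least one AE of interest at a true rate of 20%, which is 1 − 0.8^n.

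- Cohort 1, n = 10: 1 − 0.8^10 = 0.893 (stated: above 89%).
- Cohort 2, n = 15: 1 − 0.8^15 = 0.965 (stated: above 96%).

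Both reproduce. They contain no time window, so they neither support nor refute the 30-day limit.

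**2. The two definitions side by side.**

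| | Protocol 10.4.2.1 | SAP 8.2.1 |
|---|---|---|
| Window opens | after first dose | after first dose |
| Window closes | not stated | 30 days after last dose |
| AE analysis | TEAEs only | TEAEs only |
| Listings | all AEs | all AEs |

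The scope rule is the same, so narrowing the definition narrows the tables.

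**3. Days outside the window.** Assume the EOT visit falls on the day of last dose.

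- 12 weeks = 84 days: 84 − 30 = 54 days, and 54/84 = 64%.
- Read as 3 months, about 90 days: 90 − 30 = 60 days, and 60/90 = 67%.
- Against 84 treatment days plus 84 follow-up days: 54/168 = 32%.

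Protocol 8.9.1 places the first safety visit 30 to 35 days after EOT, so an event first arising on days 31 to 35 can already fall outside the window at that visit.

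**4. Weight of one participant.** 1/10 = 10 percentage points in Cohort 1, 1/15 = 6.7 in Cohort 2, 1/25 = 4 overall.

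**5. Illustration under an assumption.** The documents give no AE timing. Suppose a 20% risk were spread at constant hazard over the 168 days. The risk inside the SAP window (84 + 30 = 114 days) would be 1 − 0.8^(114/168) = 14.1%. The chance of tabulating at least one event would be 1 − 0.859^10 = 78.0% in Cohort 1 and 1 − 0.859^15 = 89.7% in Cohort 2. If AEs cluster on treatment the loss is smaller; if they come late it is larger.

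**6. Which outputs are affected.** Most summaries in SAP 8.2.3 are worded as treatment-emergent and would omit late events. The row for participants with any SAE is not so worded, although its neighbours are; yet the matching Appendix A table (3.2.1.X) is titled as a TEAE summary. The AESI text in SAP 8.2.2 and the AESI tables in Appendix A (3.2.17.X) do not use the term either. The general sentence in SAP 8.2.1 probably governs them, but the text does not settle it. No Appendix A table is set aside for events after day 30.

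**The case against.** The case for leaving the plan alone has substance.

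- **Thirty days is not foreign to the protocol.** Section 9.1.2 makes it the minimum for monitoring new AEs, and 8.9.1 puts the safety visit at 30 to 35 days. This stands as a reason for the choice, but 30 days there is a floor: 8.9.1 extends AE reporting to the follow-up visits or resolution if that is longer.
- **An open-ended window has its own bias.** Participants who relapse in follow-up may be treated as the investigator decides (Figure 1 notes), and 8.9.2 records the start of new AIHA therapy. Late events may belong to that therapy. This stands, and is why restoring the protocol's window is not the preferred remedy.
- **Late SAE collection may be selective.** Protocol 9.3.2 first requires every SAE up to the last study visit or 30 days after last dose, whichever is later. It then limits SAEs beyond 30 days to those the investigator suspects are drug-related. These rules conflict. Under the second, late SAEs should not be pooled with complete on-treatment collection without comment.
- **Listings keep everything.** Appendix A plans AE and SAE listings, and SAP 8.1 and 8.2.3 accept listings for sparse data. This also stands: what is missing is a count and a declaration, not the data.

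A reader might infer that late events vanish from every AE, SAE and AESI table. The wording of the any-SAE row and the AESI sections does not establish that. Nor does the prophylaxis rule show that the protocol expects late infections in general: it concerns PJP and says nothing about the timing of CMV, zoster or other pneumonia.

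**Conclusion.** The point holds as a reporting gap. The SAP narrows the protocol's TEAE definition, SAP 10.1 does not list the departure, and AEs that start or worsen more than 30 days after last dose would appear in no TEAE-based table. For the any-SAE row and the AESI summaries the position is ambiguous.

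The size that can be stated is 54 of 84 planned follow-up days, assuming last dose at EOT. It would be tempting to say that the tables understate incidence by 64%. The documents do not support this, because no AE timing is given and the figure is a share of days. The number of events affected is unknown. Events that began by day 30 and continue stay in, and SAP 8.2.1 keeps events whose timing is unclear. For participants in the extension the 30 days run from the last extension dose.

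The 2018 SAP is not among the documents, so when the limit was introduced cannot be said; it departs from the current protocol either way. In a descriptive study with no hypothesis tests this is a cheap improvement to the reporting of a primary safety objective, not a flaw that undermines the trial.

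**What to change.** 1. Keep the 30-day TEAE window and declare it in SAP 10.1 as a change from protocol 10.4.2.1, with the reason.
2. State in SAP 8.2.2 and 8.2.3 whether the any-SAE row and the AESI tables are treatment-emergent only, and align the Appendix A titles.
3. Add one short summary of AEs, SAEs and AESIs with onset or worsening from day 31 after last dose to end of study, by cohort and overall. Give the number of participants followed beyond day 30 as the denominator, and flag events that start after new AIHA therapy.
4. Reconcile the two rules in protocol 9.3.2 for SAEs after 30 days, and state in a footnote to the new summary what was collected.

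No new data collection is needed for the summary. The cost is some SAP wording and one extra short table. The safety figures may look slightly less favourable.

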8.2.2. Adverse Events of Special Interest

Adverse events of special interest will be summarized in the following categories by treatment and extension periods separately:

- Colitis
- CMV infection
- Diarrhea
- Exfoliative dermatitis
- Febrile neutropenia
- Herpes simplex
- Intestinal perforation
- PJP
- Pneumonia
- Pneumonitis
- Rash
- Varicella zoster virus infection

8.2.3. Adverse Event Summaries

An overall summary of AEs will include:

- Number (%) of participants reporting any TEAEs.
- Number (%) of participants reporting any SAEs.
- Number (%) of participants reporting any Grade 3 or 4 TEAEs.
- Number (%) of participants who had a TEAE leading to death.
- Number (%) of participants reporting any treatment-related TEAEs.
- Number (%) of participants who temporarily interrupted study treatment because of TEAEs.
- Number (%) of participants who permanently discontinued study treatment because of TEAEs.

The following summaries will be produced by MedDRA term (if 2 or fewer participants appear in a table, a listing may be appropriate):

- Summary of TEAEs by SOC and PT.
- Summary of TEAEs by PT in decreasing order of frequency.
- Summary of TEAEs by SOC, PT, and maximum severity.
- Summary of treatment-related AEs by SOC and PT.

- Summary of treatment-related AEs by PT in decreasing order of frequency.
- Summary of treatment-related AEs by SOC, PT, and maximum severity.
- Summary of Grade 3 or 4 TEAEs by SOC and PT.
- Summary of Grade 3 or 4 treatment-related TEAEs by SOC and PT.
- Summary of TEAEs leading to death by SOC and PT.
- Summary of treatment-emergent SAEs by SOC and PT.
- Summary of treatment-emergent SAEs by PT in descending order of frequency.
- Summary of treatment-related SAEs by SOC and PT.
- Summary of TEAEs leading to dose interruption by SOC and PT.
- Summary of TEAEs leading to discontinuation of treatment by SOC and PT.
- Summary of nonserious TEAEs by SOC and PT.
- Summary of AESI by SOC and PT.

8.3. Clinical Laboratory Tests

8.3.1. Laboratory Value Definitions

All laboratory assessments will be performed using a central laboratory, with the exception of the following, in which case the investigative site laboratory or an accredited local laboratory may be used:

- Hematology panels, including complete blood count and differential count, will be sent to a local laboratory for analysis (refer to Protocol, Section 8.2.1).
- For local laboratory assessments deemed necessary by the investigator for participant management (ie, dose modification, SAE, or COVID-19 restrictions affecting travel to the site for extension visits). Note: Such assessment data and reference ranges must be recorded in the participant's eCRF.

In the case of both local laboratory and central laboratory assessments are available, local lab will be used for analysis. Laboratory values, change from baseline values, and percent change from baseline values will be summarized descriptively by visit. Baseline values will be determined using the nonmissing values collected before the first administration, prioritizing scheduled assessments over unscheduled visits. For baseline laboratory candidates with the same date and time in the same priority category, additional rules may be provided after consultation with the medical monitor to delineate which value will be defined as baseline.

Laboratory test values outside the normal range will be assessed for severity based on CTCAE grade or similar criteria where clinical intervention is required for CTCAE grading. The incidence of abnormal laboratory values and shift tables relative to baseline will be tabulated.

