8.2.1. Hemoglobin Level, Hemolysis Markers, Direct Antiglobulin Test, and Complement Assessment

Participants will undergo hematology, serum chemistries, hemolysis markers, DAT, and complement assessment (CH50, C3, and C4) to evaluate type of AIHA diagnosis and disease status (see Table 5).

Note: For the purpose of participants' enrollment eligibility and safety and efficacy assessments, blood samples for hematology panels, including CBC and differential count, will sent to a local laboratory for analysis (see Table 5). All other Protocol-required blood samples aside from hematology panels will be sent to the central laboratory for analysis. Local laboratory

hematology panel results and central laboratory results for all other assessments will be entered into the eCRF.

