8.3.5. Laboratory Assessments

Blood draws for laboratory assessments will occur at study visits indicated in the schedule of assessments (see Table 1). Specific laboratory assessments are provided in Table 5. Blood may be drawn in pediatric tubes to minimize blood loss from phlebotomy.

All laboratory assessments will be performed at a central laboratory, with the exception of the following, in which case the investigative site laboratory or an accredited local laboratory may be used:

- Hematology panels (see Table 5), including CBC and differential count, will be sent to a local laboratory for analysis (see Section 8.2.1).
- For local laboratory assessments deemed necessary by the investigator for participant management (ie, dose modification, SAE, or COVID-19 restrictions affecting travel to the site for extension visits). Note: Such assessment data and reference ranges must be recorded in the participant's eCRF.

Extension Period:

Laboratory assessments (see Table 5) including hematology panels and hemolysis markers need to be performed in accordance with standard of care at each investigational site for the participant's condition and monitoring at the investigator's discretion and not less than every 8 to 12 weeks. Any other clinical lab monitoring should be done per the investigator's judgment for monitoring any other clinical conditions. Laboratory results will need to be documented in the eCRF.

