8.3.5.7. Serology

Anti-Streptolysin antibody, anti-phospholipid antibody, hepatitis, and HIV tests will be performed at a central laboratory (see Table 1). Hepatitis and HIV tests will be conducted during the screening period. If participants are positive for active disease, they should not be enrolled per exclusion criteria. Note: HIV screening test is optional for participants enrolled in the United States, but participants with known HIV infection enrolled in the United States will be excluded.

Table 5: Required Laboratory Analytes

Serum Chemistries	Hematology ^{a,b}	Urinalysis With Microscopic Examination	Screening Serology	Coagulation	
Albumin	CBC, including:	Color and appearance	Hepatitis B surface antigen	D-Dimer	
Alkaline phosphatase	Hemoglobin	pH and specific gravity	Hepatitis B surface antibody		
ALT	Hematocrit	Bilirubin	Hepatitis B core antibody		
AST	Platelet count	Glucose	Hepatitis C virus antibody		
Bicarbonate	RBC count	Ketones	Hepatitis C virus-RNA (only		
Blood urea nitrogen	WBC count	Leukocytes	performed if antibody positive)		
Calcium	De teum	Nitrite	HIV antibody		
Chloride	Differential count, including:	Occult blood	Anti-streptolysin antibody		
Creatinine	Basophils	Protein	Anti-phospholipid antibody		
Ferritin (screening visit and repeat at	Eosinophils	Urobilinogen			
Week 6 if participant has ongoing	Lymphocytes		Hemolysis Markers ^b		
transfusion requirements)	Monocytes	Haptoglobin (will be measured in	serum chemistry panel)		
Folic acid (screening visit)	Neutrophils	LDH (will be measured in serum chemistry panel)			
Glucose	Neutropinis	Reticulocyte count (will be measured in hematology panel)			
Haptoglobin	Absolute values must be	Hemoglobin (will be measured in hematology panel)			
Iron (screening visit and repeat at	provided for WBC differential				
Week 6 if participant has ongoing transfusion requirements)	laboratory results:	Total bilirubin ^c (will be measured	DAT and Cold Agglutinin Test		
LDH	Lymphocytes	DAT for IgG and C3d*			
Phosphate	Neutrophils	Cold agglutinin levels*			
Potassium		* Baseline and EOT			
Sodium		Other Assessments			
Total bilirubin ^c		Urinalysis			
Total protein		FSH			
Total iron-binding capacity		Urine pregnancy test (at site)			
(screening visit and repeat at Week 6		Serum pregnancy test			
if participant has ongoing transfusion	Complement assessment (CH50, C3, and C4)*				
requirements)		* Baseline and EOT			
Uric acid		Vitamin B12 (screening visit)			

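### The SAP's local-over-central laboratory rule has no analyte limit, so a management-driven local chemistry result could replace the planned central one

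*SAP*

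**What the plan says.** SAP Section 8.3.1 starts from a central default: "All laboratory assessments will be performed using a central laboratory, with the exception of the following". Two exceptions follow.

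- The first is hematology: "Hematology panels, including complete blood count and differential count, will be sent to a local laboratory for analysis".
- The second covers tests that the investigator needs to manage a participant: "For local laboratory assessments deemed necessary by the investigator for participant management (ie, dose modification, SAE, or COVID-19 restrictions". The COVID-19 part is confined to travel limits at extension visits. Under this second exception, "Such assessment data and reference ranges must be recorded in the participant's eCRF".

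The next paragraph sets the precedence rule: "In the case of both local laboratory and central laboratory assessments are available, local lab will be used for analysis". It is not limited by analyte, visit or reason for the test.

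The protocol assigns laboratories the same way. Section 8.2.1 makes hematology local and then says: "All other Protocol-required blood samples aside from hematology panels will be sent to the central laboratory for analysis". Section 8.3.5 has the same participant-management exception.

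**The concern.** Local precedence is natural for hematology, where the local result is the planned one. For serum chemistry the planned result is central, and a local result is an extra, drawn because something happened to the participant. As written, the rule prefers the extra result to the planned one.

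Two things are at stake. First, a change from baseline could compare a local post-baseline value with a central baseline, so that part of the change reflects the laboratory and not the participant. Second, the substitution would not be spread evenly. In the treatment period it would fall on participants with a dose modification or an SAE, whose chemistry a safety reader looks at most closely.

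**Working it through.** The plan gives no figure on this point, so the check is mainly a comparison of sections.

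**1. Which analytes the rule can change.** Protocol Section 8.2.1 and Table 5 give:

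| Analyte | Panel in Table 5 | Planned laboratory | Effect of the rule |
|---|---|---|---|
| Hemoglobin | Hematology | Local | Little; local is already the source |
| Reticulocyte count | Hematology | Local | Little; local is already the source |
| LDH, haptoglobin, total bilirubin | Serum chemistry | Central | Local replaces central if both exist |
| ALT, AST | Serum chemistry | Central | Local replaces central if both exist |

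For LDH, the hemolysis-marker column of Table 5 points back to the chemistry panel: "LDH (will be measured in serum chemistry panel". Footnote b of that table refers hemolysis markers to site standard of care, which matches the extension-period text in Section 8.3.5. It does not name a laboratory and does not undo Section 8.2.1.

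**2. When both values could exist in the 12-week period.** The permitted reasons for local chemistry are dose modification and SAE. Two sections make duplicates plausible:

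- Protocol Section 6.6.1 makes the Cohort 1 dose increase depend on laboratory results, on eligibility being met again at that time, and on the investigator's view of hemolysis parameters. Eligibility includes ALT/AST and creatinine clearance (Section 5.2).
- Protocol Table 4 ties interruption and restart to AST/ALT.

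Neither section requires a local chemistry panel. The local results and their ranges are recorded in the eCRF, so they would be available to the analysis.

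**3. What the baseline would be.** SAP Section 8.3.1 takes the baseline from pre-dose values and prefers scheduled to unscheduled ones. A scheduled chemistry sample is central, so the baseline is central unless a local duplicate exists there too.

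**4. Which outputs use these values.**

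- Chemistry summaries, and the shift tables by CTC grade (SAP Appendix A, Tables 3.3.2.X and 3.3.4.X).
- Low/normal/high counts by visit (SAP Section 8.3.2).
- The secondary endpoint on normalization of hemolytic markers (SAP Section 7.4, item 6; Table 2.2.6).
- Pharmacodynamic change from baseline (SAP Sections 2.2 and 7.7).

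The last two rest on inference: the rule stands in the safety section, and SAP Section 7 neither cites it nor gives another. The SAP has no rule to keep baseline and post-baseline in one laboratory, does not say whose range defines normalization, and plans no sensitivity analysis on central values.

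**5. Which outputs do not.** SAP Section 7.2 defines CR and PR by hemoglobin and time since transfusion. SAP Section 10.1 records that the hemolysis component was removed. Hemoglobin is local throughout, so the SAP's primary endpoints do not depend on the rule.

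**6. Scale.** The documents give neither the number of duplicates nor any local-central difference. Suppose k participants had a normalization status that depended on the laboratory. The proportion moves by 100 × k/n points:

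| k (assumed) | Cohort 1, n = 10 | Cohort 2, n = 15 | Overall, n = 25 |
|---|---|---|---|
| 0 | 0 | 0 | 0 |
| 1 | 10.0 | 6.7 | 4.0 |
| 2 | 20.0 | 13.3 | 8.0 |
| 3 | 30.0 | 20.0 | 12.0 |

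This shows how sensitive a small cohort is. It does not estimate what will happen.

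**The case against.** The case against runs as follows.

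- **Duplicates are not shown.** Local chemistry is permitted, not scheduled, and the rule acts only when both values exist. The listed dose-increase criteria are transfusion need and hemoglobin change. Protocol Section 6.6.1 also lets the increase wait until between Weeks 6 and 8, or Week 8 itself, which leaves time for central results. This stands: the effect is possible, and its frequency is unknown.
- **Ranges are partly handled.** Local reference ranges must be recorded, and SAP Section 8.3.2 classifies results against available normal ranges, so each value can be judged by its own range. This stands for most of the classification worry. It does not help a numeric change from baseline, and the SAP still does not say which range applies to normalization.
- **Nothing is lost from the record.** Central results are still entered in the eCRF, and serum chemistry is listed (Listing 3.3.2). This stands: only the value that is summarized is at issue.
- **The analyses are descriptive.** SAP Sections 3.2 and 7 call them exploratory, with no p-values. This limits the consequences but does not make the wrong value a better summary.
- **The rule may have been meant for hematology.** SAP Section 10.2.1 says that Section 8.3.1 was updated to match Protocol Amendments 3 to 5. Those amendments clarified local hematology and allowed local testing for COVID-19 travel limits at extension visits. Neither calls for replacing an available central chemistry value. That reading is plausible, but the text does not say it.

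A reader might also infer that the COVID-19 exception spreads the problem across the extension. The documents do not support that. Extension laboratory work already follows site standard of care, with safety analytes tested locally (Protocol Sections 8.3.5 and 8.8), so a paired central value is unlikely and the rule would rarely act.

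**Conclusion.** The point holds as a wording defect with a limited and unquantified effect. SAP Section 8.3.1 gives local results precedence for every analyte, although the protocol plans serum chemistry as central. In the 12-week period any duplicates would come from participants with a dose modification or an SAE, and a local value would then usually be set against a central baseline. The exposed outputs are the chemistry summaries and shift tables and, if the rule carries over to SAP Section 7, the normalization endpoint and pharmacodynamic changes from baseline.

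Stronger readings are tempting, and the documents do not support them:

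- *The markers will switch laboratory at dose-decision and SAE visits.* The text permits this; it does not plan it.
- *The primary response is at risk because Week 6 opens its window.* CR and PR in the SAP use only hemoglobin, which is local by design, and transfusion timing.
- *All 10 Cohort 1 participants could be affected.* Ten is only the cohort size. Participants with a meaningful response and no transfusion need at Week 6 do not meet the dose-increase criteria.
- *Results will flip between normal and abnormal.* That presumes a value is judged against another laboratory's range, which the SAP does not say.

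The conclusion rests on reading the precedence sentence literally and, for the efficacy and pharmacodynamic markers, on the absence of any other rule in SAP Section 7.

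**What to change.** Replace the precedence sentence in SAP Section 8.3.1 with a rule to this effect:

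> Local results take precedence for hematology panels only. For all other analytes the central result is used when available. A local result is used only when the central result is missing; it is then flagged and classified against its own recorded reference range.

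Apply the rule to baseline as well as post-baseline values, and say in SAP Section 7 that it also governs the hemolytic-marker and pharmacodynamic analyses.

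This will not remove laboratory mixing where no central result exists, as in much of the extension, but the flag will make it visible. The cost is one SAP sentence with a cross-reference, and one programming rule. It needs no new data and changes no aspect of participant management.
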